## 1.0 PROTOCOL SUMMARY AND/OR SCHEMA

This is a multi-center, open-label, phase 2 trial testing the efficacy and safety of 2 interventions that target rash during PI3K inhibitor therapy in postmenopausal women and men with histologically-confirmed, hormone receptor (HR)-positive, HER2-negative, PIK3CA mutant metastatic breast cancer (MBC). A total of 63 patients will be enrolled into one arm: benralizumab 30mg in combination with standard of care (SOC) endocrine therapy (fulvestrant or AIs or aromatase inhibitors (AIs)) and PI3K inhibition (alpelisib). A total of 43 patients will be enrolled at MSKCC and a total of 20 patients will be enrolled at the participating external institutions (10 patients at Stanford University and 10 patients at Dana Farber Cancer Institute). The primary endpoint is the proportion of patients with grade  $\leq 1$  rash rate at 4 weeks.

**Patient Population:** The primary study population will be postmenopausal women and men with histologically-confirmed, HR-positive, HER2-negative, *PIK3CA* mutant MBC who have received no more than 2 lines of endocrine-based therapy in the metastatic setting.

**Design:** A multi-center, open-label, phase 2 trial testing the efficacy and safety of one interventions (one anti IL-5 receptor antibody and one antihistamine) that target the maculopapular rash during PI3K inhibitor therapy in patients with HR-positive, HER2-negative, *PIK3CA* mutant MBC receiving first or second line therapy. Study participants (n=112) will enrolled to one arm: benralizumab (anti-IL5ra) in combination with SOC endocrine therapy (fulvestrant or AIs) and PI3K inhibition (alpelisib). The primary endpoint is the grade  $\leq 1$  rash rate at 4 weeks. The study size is determined to compare the grade  $\leq 1$  rash rate at four weeks with historical controls. It has been reported that approximately 34% of patients receiving alpelisib will develop  $\geq$  grade 2 rash within the first 30 days. The corollary is that 66% of historical controls will have grade  $\leq 1$  rash within the first 30 days. An increase in rash control to approximately 88% is deemed to be clinically meaningful with the investigational agent under investigation (IL5r antibody). A sample size of 57 patients per group will achieve an 80% power to detect an odds ratio of 4.0 with respect to the primary endpoint. The proportion in the experimental group is assumed to be 0.66 under the null

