### **7.2 Randomization**

No randomization will occur in this study. After eligibility is established and immediately after consent is obtained, patients will be registered in the Clinical Trials Management System (CTMS).

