## 12.0 CRITERIA FOR REMOVAL FROM STUDY

- 1) > 2 consecutive weeks of a delay in treatment due to toxicities
- 2) Progressive disease (breast cancer)
- 3) Unacceptable toxicity
- 4) Intercurrent, non-cancer related illness that prevents continuation of protocol therapy or follow-up
- 5) Major protocol violation that would render the patient inevaluable for efficacy
- 6) Repeated non-compliance by the patient with protocol requirements
- 7) Changes in the patient's condition or study intervention related toxicity such that, in the opinion of the investigator, continued participation in the protocol would compromise patient well-being
- 8) Withdrawal of patient's consent for personal reasons
- 9) Death

We do not expect any of the above criteria to occur with high frequency as the 4 week PFS for this population is over 90%. All participants for whom we are able to obtain the 4 week primary endpoint (had rash event prior to 4 weeks) will be considered evaluable for the primary rash endpoint under the intention-to-treat (ITT) approach.

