## 14.0 BIOSTATISTICS

### Sample Size

This will be a single arm trial. The target sample size is intended to test the hypothesis that benralizumab reduces the frequency of grade  $\geq$  grade 2 rash at 4 weeks relative to the historical controls in patients receiving alpelisib. The primary endpoint in the current study will be the proportion of patients to achieve a rash grade of 1 or less. It has been reported that approximately 34% of patients receiving alpelisib will develop  $\geq$  grade 2 rash within the first 30 days. An increase in rash control to approximately 88% is deemed to be clinically meaningful with the investigational agent. Sample sizes of 57 patients achieves an 80% power to detect a difference based on a two sample proportions test. Due to potential attrition during the course of the study, the sample size will be increased by 10%. The resultant sample size will be 63 patients.

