### General Statistical Plan

There will be one analysis population for the current study. The modified intent to treat (ITT) population will be all patients regardless of treatment compliance for whom investigators were able to obtain a 4-week efficacy assessment. The safety population will be patients who received at least one dose of study drug or the standard of care, regardless of any efficacy assessments. All efficacy analyses will be based on the modified ITT population. Patient, clinical and safety data as well as primary, secondary and exploratory endpoints will initially be presented descriptively as means, medians, or proportions with appropriate measures of variance (i.e. range, SD, 95%CI). The primary endpoint,  $\geq$  grade 2 rash versus  $<$  grade 2 rash will be evaluated using generalized linear models (GLIM), with a logit link function and a Bernoulli distribution. A group\*time interaction will be included to assess the difference in the outcome measure at the specific study time points. Differences in the frequency of grade 0/1 rash overall all study visits (days 14, 28 and 90) will be assessed using mixed models for repeated measures as a secondary analysis.

The total number of dose reductions and delays between study groups over the trial period will be compared using Poisson regression analysis. The absolute difference in the FACT-B and PRO-CTCAE scores from day 1 to 14 and 28 between groups will be also be evaluated using repeated measures mixed models. The cumulative dose of corticosteroid use between

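### The primary analysis of this single-arm trial is a group-by-time model with no second group, and no test against 0.66, alpha or success rule is prespecified

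*Combined protocol and SAP*

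**What the plan says.** Section 7.2 states "No randomization will occur in this study" and Section 14.0 (Sample Size) states "This will be a single arm trial". All 63 patients receive benralizumab. The primary objective in Section 2.0 is a comparison of rash incidence with historical controls.

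The benchmark rests on one statement in Sample Size: "It has been reported that approximately 34% of patients receiving alpelisib will develop" rash of grade 2 or worse in the first 30 days. Its complement is 66%. Section 1.0 gives the hypotheses: "The proportion in the experimental group is assumed to be 0.66 under the null", and 0.88 under the alternative. For power, Sample Size says "Sample sizes of 57 patients achieves an 80% power to detect a difference based on a two sample proportions test". Section 1.0 makes clear that this is a per-group figure: "A sample size of 57 patients per group will achieve an 80% power to detect an odds ratio of 4.0".

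The General Statistical Plan does not carry that test forward. It specifies a logistic model for the primary endpoint, in which a group*time "interaction will be included to assess the difference in the outcome measure at the specific study time points". A 95% CI appears there only as one of several descriptive measures and is not linked to 0.66.

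Section 13.1 defines the endpoint as grade 1 or less at 4 weeks, and Section 11.0 puts that visit at day 28 ± 7. Section 12.0 points towards a cumulative reading, since it counts as evaluable those for whom "we are able to obtain the 4 week primary endpoint (had rash event prior to 4 weeks").

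**The concern.** The primary question is a contrast with patients outside the trial, and the planned model can supply that contrast only if those patients are in the dataset. None are designated. Section 3.3 (alpelisib safety population, n=284) and Section 3.4 (more than 100 patients at the lead centre) describe alpelisib series but do not name either as the control.

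Two things are at stake. First, the choice between a one-sample test and a two-sample test against some cohort is left open in an open-label trial. If it is made once outcomes are known, it can decide the verdict near the threshold. Second, if the endpoint is status at the week 4 visit, any grade 2 or worse rash that resolves before the visit counts as a success here but as a failure in the 30-day benchmark. That favours the drug.

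A lesser matter is that the secondary analyses carry the same multi-arm wording. There are between-group Poisson, mixed-model and Yates chi-square comparisons, a Wilcoxon test that names only the benralizumab group, and a comparison with antihistamines, which the trial does not give. The log-rank and Cox sentence names no groups and becomes a historical-control contrast only through secondary objective 4.

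**Working it through.** **Inputs.** From Sections 1.0 and 14.0: p0 = 0.66, p1 = 0.88, 57 evaluable, 63 enrolled. The documents give no alpha, control size or share of rashes that resolve; the values used below are assumptions.

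**1. Can the model be fitted?** With T visits, an intercept, a group term, T−1 time terms and T−1 group*time terms make 2T columns. With one group the rank is T. Group and group*time are therefore aliased with the intercept and time terms, whatever T is.

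**2. The plan's own figure.** Pooled two-sample test, two-sided 0.05, 80% power:

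n per group = [1.96·√(2·0.77·0.23) + 0.8416·√(0.66·0.34 + 0.88·0.12)]² / 0.22² = (1.1665 + 0.4835)² / 0.0484 = 56.2, so 57.

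Power is 0.805 at 57 per group and 0.798 at 56. Other variants give other sizes: one-sided 0.05 gives 45 (53 with continuity correction), and two-sided 0.05 gives 54 unpooled, 55 arcsine, 62 log-odds and 66 with continuity correction. Attrition: 57 × 1.10 = 62.7, so 63. The stated 80% thus belongs to a comparison of 57 treated patients with 57 controls.

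**3. Power if the comparison is made another way (57 treated).**

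| Comparison | Power at 0.88 |
|---|---|
| Two-sample, 30 controls | 0.678 |
| Two-sample, 57 controls | 0.805 |
| Two-sample, 100 controls | 0.886 |
| Two-sample, 284 controls | 0.959 |
| Exact one-sample against 0.66, one-sided 0.025 | 0.984 |

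The one-sample rule is the smallest r with P(X ≥ r | 57, 0.66) ≤ 0.025. That is r = 45 (size 0.0240; 44 gives 0.0468). The Clopper-Pearson 95% lower limit is 0.661 at 45/57 and 0.642 at 44/57.

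**4. Does the choice of test matter?** Hold the control result fixed near 66%, find the count out of 57 that a two-sided 0.05 pooled z-test needs, and compare it with 45. The last three columns give the probability, under Binomial(57, p), that the two tests disagree.

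| Assumed controls | Two-sample needs | p = 0.66 | p = 0.80 | p = 0.88 |
|---|---|---|---|---|
| 20/30 | 49 | 0.023 | 0.484 | 0.224 |
| 38/57 | 48 | 0.022 | 0.381 | 0.124 |
| 66/100 | 47 | 0.019 | 0.258 | 0.058 |
| 187/284 | 46 | 0.013 | 0.126 | 0.020 |

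**5. Benchmark against endpoint.** Suppose the drug does nothing and a share r of the 34% with grade 2 or worse rash is back to grade 1 or less at the visit. The success rate at the visit is then 0.66 + 0.34r.

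| r | Rate at visit | P(X ≥ 45 of 57) |
|---|---|---|
| 0 | 0.66 | 0.024 |
| 0.10 | 0.694 | 0.074 |
| 0.25 | 0.745 | 0.274 |
| 0.50 | 0.83 | 0.840 |

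Some resolution by week 4 is plausible on the protocol's own text: Section 3.4 gives a median onset of 13 days for grade 3–4 rash, and Table 2 lists a 10-day steroid course for grade 3.

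**The case against.** The best defence is that the comparator is unidentified, not absent. The null and alternative values are written down, about 88% is called clinically meaningful, and a 95% CI is planned, so a reader could set that interval beside 0.66. With patient-level historical controls entered as the second group, the model could be fitted. Alpha is unwritten but can be inferred, because among the variants tried only a pooled two-sided 0.05 test gives exactly 57.

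The largest disagreement figures need a true rate of 0.80 and control series of 30 or 57, none of which the plan mentions. At 0.88, with series of the sizes it does mention, disagreement is 6% (100) or 2% (284), and under the null it is 1–2%. The calculation also ignores sampling variation in the controls. The resolution shares have no source, and on a cumulative reading of the endpoint most of the mismatch disappears. The trial calls itself exploratory, and the sample is ample against a fixed 0.66.

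These points limit the size of the problem without removing it. Nothing links the interval to 0.66, no control dataset is designated, and an alpha inferred from a sample size is not a stated rule. The exploratory label is used to waive multiplicity adjustment, while the sizing text still presents the trial as testing a hypothesis. The leftover multi-arm wording in the secondary analyses should carry no weight in the severity.

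**Conclusion.** The concern holds and must be fixed. As written, the primary model cannot be estimated from the trial's data, the sizing test has no second sample, and no result is defined in advance as success. The stated 80% power describes a 57 versus 57 comparison that the trial will not make. Depending on the comparison eventually chosen, power at 0.88 runs from 0.68 to 0.98.

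The sample is not too small. What is missing is a prespecified, executable test. The aliasing, the reproduction of 57 and the absence of any stated rule do not depend on assumptions. The power range, the disagreement probabilities and the 7%, 27% and 84% false-success rates do: they rest on an assumed alpha, control size or resolution share, and the false-success rates apply only if the endpoint is status at the visit.

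**What to change.** 1. Align the definitions first. Either test freedom from grade 2 or worse rash at any time through week 4, with the window fixed, or re-derive the benchmark for rash status at week 4.
2. Make the primary analysis an exact one-sample binomial test against that benchmark, stating alpha and sidedness, with a Clopper-Pearson 95% CI. Because the evaluable number may vary, give the cut-off for each n. For example, at an assumed one-sided 0.025 against 0.66:

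| Success if at least | Size | Power at 0.88 |
|---|---|---|
| 43/54 | 0.0212 | 0.976 |
| 45/57 | 0.0240 | 0.984 |
| 48/60 | 0.0130 | 0.976 |
| 50/63 | 0.0149 | 0.984 |

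3. Restate the power for that test, and report the source and sample size of the 0.66.
4. Remove the group, group*time and antihistamine terms. Report secondary endpoints as within-arm estimates with 95% CIs, and FACT-B and PRO-CTCAE as within-patient change over time.

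The alternative to step 2 is to name, before outcomes are analysed, the historical cohort, its size, its endpoint definitions and the comparison method, and to restate power for that control size.

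The cost is a protocol amendment to Section 14.0, the Section 1.0 summary, and the affected objectives and endpoints in Sections 2.0, 3.7 and 13.2. No new patients or visits are needed. There are two drawbacks. Without a named cohort the secondary endpoints become descriptive. The one-sample test also treats 0.66 as known without error: if the true historical rate were 0.70 or 0.75, the 45/57 rule would have a type I error of 0.089 or 0.303. That is why the source of the benchmark must be reported.

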hypothesis and 0.88 under the alternative hypothesis. The proportion is 0.66. If it is assumed that 10% of patients will withdraw consent or be lost to follow up, then 63 patients will need to be enrolled into this trial.

**Treatment Plan:** All participants will receive SOC endocrine therapy (fulvestrant or AIs) and PI3K inhibition (alpelisib). Participants will receive benralizumab 30mg subcutaneously on day -1. All participants will be monitored at regular visits for the duration of the trial. After 4 weeks, patients will be followed for safety at 90 days and disease progression for 1 year.

**Estimated Time to Completion:** 1 years.

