### Alpelisib

The recommended dose modifications for adverse reactions (ARs) are listed in Table 1.

Table 1. Alpelisib dose reduction guidelines

Alpelisib dose level	Dose and schedule	Number and strength of tablets
Starting dose	300 mg once daily	Two 150 mg tablets OR ALTERNATIVELY One 200mg and two 50mg tablets can be used to reach the 300 mg dose level
First dose-reduction	250 mg once daily	One 200 mg tablet and one 50 mg tablet
Second dose-reduction	200 mg once daily 	One 200 mg table

If further dose reduction below 200 mg once daily is required, discontinue alpelisib

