## Diarrhea

Memorial Sloan Kettering Cancer Center  
 [name]  
 [name]

Table 7. Dose modification and management for diarrhea.

Grade	Recommendation
Grade 1	No dose adjustment is required.
Grade 2	Initiate or intensify appropriate medical therapy and monitor as clinically indicated. Interrupt alpelisib dose until recovery to Grade $\leq$ 1, then resume at same dose level.
Grade 3 and 4	Initiate or intensify appropriate medical therapy and monitor as clinically indicated. Interrupt alpelisib dose until recovery to Grade $\leq$ 1, then resume at the next lower dose level.

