the Benralizumab group over the study period will be compared using the Wilcoxon Rank Sum test. Time to the development of grade 1 or 2 rash will be evaluated using Kaplan-Meier time to event curves and assessed using the log rank test and Cox proportional hazards regression analysis. The Yates corrected chi square test will be used to compare the frequency of non-skin alpelisib related adverse events between groups, as well as 6 and 12 month ORR and PFS. Differences between the Benralizumab group on IL-5 inhibition and antihistamines and non-skin alpelisib related adverse events will be evaluated using linear mixed models. Changes in inflammatory biomarkers in skin and related to rash and all other exploratory endpoints will only be evaluated graphically with descriptive statistics. Given the exploratory nature of the current trial, there will be no adjustments for multiplicity. All the statistical analyses will be performed using SAS® Version 9.4 or higher. De-identified data will be shared via MSK secured e-mail quarterly to Augmentium Pharma Consulting for statistical analysis.

Patients may be removed from the study for various reasons as outlined in section 12.0 of the protocol. Descriptive statistics will be reported separately for patients removed from the study, including a summary of reasons for removal, their median duration in the study and range, median, range, and the distribution of rash grades at all follow-up times prior to their removal from the study.

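### The Poisson comparison of dose reductions and delays allows neither for variance differing from the mean nor for unequal exposure, so its standard error may be miscalibrated in either direction

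*Combined protocol and SAP*

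**What the plan says.** The General Statistical Plan in Section 14.0 reads: "The total number of dose reductions and delays between study groups over the trial period will be compared using Poisson regression analysis". It does not say whether reductions and delays are summed or modelled separately, and it does not mention overdispersion, a robust variance or an offset. The same section says "This will be a single arm trial" and "Given the exploratory nature of the current trial, there will be no adjustments for multiplicity". No significance level is stated anywhere.

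The dose rules that generate the counts are in Section 10.0:

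- **Hold and reduction from one toxicity:** grade 3-4 diarrhea (Table 7: after recovery, "then resume at the next lower dose level"), other grade 3 toxicity (Table 8, same wording), and a second or third grade 3 hyperglycemia (Table 3).
- **Hold only:** grade 2 diarrhea (Table 7), and a first grade 3 hyperglycemia that recovers within 3 to 5 days (Table 3).
- **Hold, no reduction stated:** grade 3 rash (Table 2), where the restart is left to the package insert.
- **Ceiling:** the Table 1 footnote says "If further dose reduction below 200 mg once daily is required, discontinue alpelisib", which allows at most two reductions per patient.
- **Early end of exposure:** grade 4 rash and grade 4 other toxicity end alpelisib (Tables 2 and 8). Section 12.0 removes patients whose treatment is delayed for toxicity by more than two consecutive weeks.

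**The concern.** A Poisson model takes its standard error from the assumption that the variance of each patient's count equals the mean. If one toxicity adds 2 to a summed count, or if some patients are toxicity-prone and others are not, the variance exceeds the mean and the interval is too narrow. If most toxicities occur at most once and give a hold only, or if the ceiling on reductions binds, the variance can fall below the mean and the interval is too wide. Patients who leave alpelisib early have less time in which to be counted. Without an offset they look like patients who tolerated treatment well.

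At stake is any claim that benralizumab reduced dose modifications. Secondary objective 1 is defined through relative dose intensity over the first 4 weeks, but Section 14.0 names no test for that quantity. The Poisson sentence is therefore the only inferential method given for dose modification.

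**Working it through.** **1. The plan's own figure and the significance level.** The plan gives no error rate for the Poisson comparison. Its only related figure is the sample size: "Sample sizes of 57 patients achieves an 80% power to detect a difference based on a two sample proportions test". With proportions 0.66 and 0.88, two-sided 5%, pooled variance and no continuity correction:

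n = [1.96·√(2·0.77·0.23) + 0.8416·√(0.66·0.34 + 0.88·0.12)]² / 0.22² = (1.1665 + 0.4835)² / 0.0484 = 56.2, so 57 per group (power 0.805).

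The one-sided version gives 45, and a continuity correction gives 66. Then 57 × 1.1 = 62.7, which gives 63. A two-sided 5% level reproduces the stated figure, so it is assumed below.

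**2. Pairing alone.** Let toxicities follow a Poisson distribution, and let a share q of them add both a hold and a reduction to one summed count. Each toxicity then contributes 1 + q on average, with mean square (1 − q) + 4q = 1 + 3q. So variance/mean is φ = (1 + 3q)/(1 + q), and the actual size of a nominal 5% test is 2·[1 − Φ(1.96/√φ)].

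| q | φ | actual size | with at most two reductions (simulated, 0.6 toxicities per patient) |
|---|---|---|---|
| 0.12 | 1.21 | 7.5% | 7.2% |
| 0.25 | 1.40 | 9.8% | 9.3% |
| 0.50 | 1.67 | 12.9% | 12.2% |
| 1.00 | 2.00 | 16.6% | 14.9% |

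Solving backwards with q = (φ − 1)/(3 − φ), doubling to 10% needs φ = 1.42 and q = 0.27. Tripling to 15% needs φ = 1.85 and q = 0.74.

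**3. The documents' rates.** From Section 15.0, with the 284 alpelisib patients of Section 3.3 as denominator: grade 3 hyperglycemia 33% (taken as hold only), grade 2 diarrhea (71 − 19)/284 = 18.3% (hold only), grade 3 diarrhea 19/284 = 6.7% (hold plus reduction). The paired share is 0.067/(0.33 + 0.183 + 0.067) = 0.12. If each occurs at most once and independently:

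- mean = 0.33 + 0.183 + 2(0.067) = 0.65
- variance = 0.33·0.67 + 0.183·0.817 + 4·0.067·0.933 = 0.62
- φ = 0.96, simulated size 4.4%.

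There is no inflation here, because events that occur at most once have variance below their mean and this offsets the pairing. Adding assumed grade 3 rash (0 to 20%, with or without a reduction) and other grade 3 toxicity (0 to 30%) gives 3.9% to 8.7%.

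**4. Clustering within patients.** In the same rule-based model with an assumed latent correlation of 0.3 between toxicities, the size is 7.4% to 16.7%. In the model of step 2 with no pairing, assumed gamma heterogeneity of variance 0.5 or 1 gives 8.1% or 11.7%. The largest value in any run, 21.6%, needs heterogeneity variance 1 and every toxicity paired, which the hold-only rules exclude.

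**5. Fixed historical rate.** A one-sample Poisson test of 57 patients against a fixed rate gives 9.5%, 13.2% and 17.1% at q = 0.25, 0.5 and 1. The variance problem does not depend on having a patient-level comparator.

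**6. Effect of the fix.** With quasi-Poisson or sandwich standard errors, size returned to 4.5% to 5.6% in every two-group scenario run.

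**Limits.** The toxicity rates cover the whole of treatment, not 4 weeks. Step 3 omits grade 4 hyperglycemia (3.9%) and recurrences, and recurrences would raise the dispersion. These runs gave every patient equal follow-up, so they do not measure the effect of the offset. The case for it rests on the stopping and removal rules.

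**The case against.** The strongest objection is to the size of the problem. A reader might infer from Tables 7 and 8 that holds and reductions generally come in pairs, so that the test rejects at two to three times its nominal rate. The documents do not support that. The commonest severe toxicity with a stated rate, grade 3 hyperglycemia, is hold only at a first occurrence with prompt recovery. Grade 2 diarrhea is hold only, and no reduction is written for grade 3 rash, the target toxicity.

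Nor can one conclude that the interval is necessarily too narrow over the first 4 weeks. Median onset of grade 2-3 diarrhea is day 46. The reduction for persistent grade 2 hyperglycemia needs 21 days without recovery, after a median first onset of 15 days (15 + 21 = 36, beyond day 28). All of this stands.

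It is also fair to say that the plan is silent rather than explicit. Poisson regression can be run with a scale or robust option, and separate models for reductions and for delays would remove the pairing mechanism. But the natural reading of the sentence is one total, separate models would not remove clustering within patients, and an unstated option is not prespecified.

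A further objection is that the sentence has a more basic gap: one arm, and no described patient-level historical counts. That is correct. Better standard errors do not supply a comparator.

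**Conclusion.** The point holds in a limited form. Nothing in the plan ensures that the count's variance equals its mean, and nothing adjusts for unequal time on alpelisib. The p-value and interval may therefore be miscalibrated; it would go too far to call them invalid outright. At an assumed two-sided 5% level and for a summed count, the false-positive rate is about 4% to 9% under the documents' rates with independent single toxicities and the assumed additions. About 7% to 17%, up to roughly threefold, requires clustering within patients or a large assumed pairing share (27% for doubling, 74% for tripling). The downward departure in these runs was small (3.9% at the lowest), while the upward one could matter.

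The consequence is contained. This is a secondary analysis without multiplicity adjustment, and the primary rash endpoint is unaffected. The change is still worth making because the dispersion cannot be known in advance and the protection costs almost nothing.

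**What to change.** In Section 14.0, keep the Poisson (log-linear) model and add that standard errors will be robust (sandwich) or quasi-Poisson, naming one of them. Add that the log of days on alpelisib will be the offset, and that the rate will be reported with its robust 95% confidence interval. State whether reductions and delays are summed and how days on hold enter the offset.

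The cost is a sentence or two of text and an option in the SAS procedure. Intervals may be slightly wider. No new data are needed, because compliance records and dosing diaries are already collected.

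Two matters lie outside this change. The comparator meant by study groups in a single-arm trial must be defined separately; the variance provision is needed whether it is patient-level controls or a fixed historical rate. Limiting the count to 28 days, or counting a hold and its following reduction as one episode, would redefine the endpoint. Those are choices for the sponsor and are not needed to correct the standard error.
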